5.1.5. Analysis of HRCT Data

HRCT images that meet the quality control standards as assessed by the independent radiology imaging group will be considered for the analyses.

5.2. Analysis Sets

5.2.1. Intent-to-Treat Population (ITT)

The intent-to-treat population includes all randomized subjects. Subjects will be analyzed according to their randomized treatment arm regardless of the actual study treatment received.

5.2.2. Per-Protocol Set (PPS)

The per-protocol set is defined as all randomized subjects who have completed at least 36 weeks of treatment, with baseline and at least one post-baseline PFT assessment, and no major protocol deviation(s) that significantly impact efficacy analyses.

5.2.3. Safety Analysis Set (SAF)

The safety analysis set includes all subjects who have received any study drug. Subjects will be analyzed according to the treatment actually received.

5.2.4. Immunogenicity Analysis Set (IGS)

The IGS will include all subjects who are in the SAF and have a baseline evaluable immunogenicity assessment and at least 1 post-baseline evaluable (i.e., positive, negative) immunogenicity assessment.

5.3. General Data Handling Rules and Presentation Specifications

5.3.1. Analysis Period

5.3.1.1. On-Study Period

Unless otherwise specified, the efficacy analysis will be based on the on-study period, which includes all data collected during the double-blind period.

For the safety analysis, all safety assessments beyond 60 days of the last dose will be excluded from summary tables or figures.

Confidential Page 17 of 56

5.3.1.2. On-Treatment Period

The on-treatment analysis includes only the assessments that are observed during on-study period as defined above (Section 5.3.1.1), but within 3 weeks after the last study drug infusion in the double-blind period.

5.3.2. Baseline Definitions

Baseline for PFTs is defined as the last "Best" PFT (from the Over-Reader) before the first study drug infusion (or randomization date if no infusion is received) (Section 5.1.4).

Baseline for all other endpoints is defined as the last measurement prior to the first study drug infusion (or randomization date if no infusion is received). Unscheduled visits will be considered for baseline.

5.3.3. Formulas

- Study Day Calculation
 - The day when a subject receives the first dose of study drug after randomization is designated as Day 1. For subjects who have not received any study drug in an ITT analysis, their randomization date will be used as Day 1.
 - Study day of an assessment/procedure is calculated as follows.
 - For assessments or procedures on Day 1 or later:
 Study day = assessment/procedure date Day 1 date + 1
 - For assessments or procedures earlier than Day 1: Study day = assessment/procedure date - Day 1 date
- Body Mass Index (BMI) = $\frac{Weight (kg)}{Height (cm)^2}$
- Body weight, height, and temperature will be converted using the following formula:
 - -kg = lb/2.2
 - $-cm = 2.54 \times in$
 - ${}^{o}C = (5/9) \times ({}^{o}F 32)$
- Absolute Change from Baseline = *Value at Post-baseline visit baseline value*
- Relative change from baseline (%) is derived with the formula below:

$$\frac{\textit{Value at Post baseline visit} - \textit{Baseline value}}{\textit{Baseline value}} \times 100$$

5.3.4. General Instructions of TLF

• For continuous variables that are recorded as "<X" or ">X", the value of "X" will be used in the calculation of summary statistics.

Confidential Page 18 of 56

- All reporting values (mean, median, SD, SE, LSMean, 95% CI, etc.) for the continuous variables will have 1 additional decimal place than raw data. Min and Max will have the same decimal place as raw data.
- All percentages will be rounded to one decimal place. The percentage will be suppressed when the count is zero. All durations of time will have 1 decimal place.
- All tables and listings will have a header showing "FibroGen, Inc.", the protocol number (ZEPHYRUS 2), date of data cutoff, and Page x of y. A footer will show the program file path/name, output file path/name, date of data extraction, run date, and run time

5.3.5. Handling of Dropouts or Missing Data

All assessments collected will be considered for analyses regardless of whether such data were collected during treatment or after a subject discontinued treatment. All analyses assume the missing data are missing at random (MAR), unless stated otherwise. Detailed missing data handling is described in the analysis of specific endpoints.

5.4. Interim Analyses and Data Monitoring Committee

In addition to routine safety monitoring, an independent DMC will be established to review safety data on an ongoing basis. A DMC charter will establish the procedures, meeting frequency, and scope of responsibilities of the committee.

This study has no planned or pre-specified interim analysis for either efficacy or futility.

5.5. Analysis Visit Window

Analysis visits, instead of the nominal visits from case report form (CRF), derived from visit dates and visit time windows will be used in the by-visit analyses. Unscheduled visits within a visit window (defined in Appendix 2) will be grouped into the closest scheduled visits based on the visit date. For subjects who have more than one measurement at a certain analysis visit, the last measurement will be used, with the following exceptions:

- Liver function tests, such as Alanine Aminotransferase (ALT), Aspartate Aminotransferase (AST), Gamma-Glutamyltransferase (GGT), Alkaline Phosphatase (ALP), and total bilirubin, in which the maximum value will be used.
- Spirometry data: the best value to be used for analysis as defined in Section 5.1.4.
- Vital signs: the values on the infusion days will be used if applicable.
- ADA assessment: select in the order of 1) last ADA+ assessment; 2) earlier ADA+ assessment; 3) last ADA- assessment.

Confidential Page 19 of 56

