2.6.2. Dose Rationale

Pamrevlumab has been tested in a Phase 1 single-ascending dose study (FGCL-MC3019-002) and two repeat-dose Phase 2 studies (Study 049 and Study 067) in IPF patients. The single-dose study utilized intravenous infusions of 1, 3, or 10 mg/kg. Study 049 was an open-label study testing 15 mg/kg and 30 mg/kg every 3 weeks for 45 weeks as monotherapy. Study 067 was a placebo-controlled study testing 30 mg/kg every 3 weeks for 45 weeks as monotherapy. All studies collected safety and tolerability data, samples for pharmacokinetic analyses and pulmonary function test measurements.

Prior to studying IPF, pamrevlumab was tested in a Phase 1 multiple ascending dose study in combination with gemcitabine and erlotinib in advanced pancreatic cancer patients using IV doses of 3 mg/kg up to 45 mg/kg every 2 weeks, and weekly doses up to 22.5 mg/kg. The Phase 1 study in pancreatic cancer included assessments of safety and tolerability, samples for pharmacokinetic analyses and measures of disease progression.

Collectively these studies have investigated repeat doses up to 30 mg/kg every three weeks in IPF and up to 45 mg/kg every 2 weeks in pancreatic cancer. The doses in all studies were found to be safe and tolerable and active doses were identified in each indication.

The combined data were analyzed via population pharmacokinetics (PopPK) to determine if the PK for the two indications were similar. The combined PopPK model was used to derive steady state trough exposures of pamrevlumab leading to exposure-response relationships for the two Phase 2 IPF studies. The efficacy measure was forced vital capacity FVC_{pp}. Clinical trial simulations of FVC_{pp} were also performed to evaluate the probability of success of

pamrevlumab versus placebo at different doses. Safety data for the two Phase 2 IPF studies were tabulated by dose group, and exposure-response relationships were explored for selected adverse events. These analyses form the basis for the Phase 3 dose in IPF patients and shows that an IV administration of 30 mg/kg of pamrevlumab every three weeks to IPF patients achieves better efficacy than placebo for FVCpp, and reaches the mean pamrevlumab trough where efficacy begins to plateau (approximately 150 µg/mL).

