6.1.2. Treatment Period

The study procedures and assessments are presented for the Treatment phase in [Appendix 1](#).

The treatment period begins on Day 1 (first study drug infusion) and continues through Week 48. Visit windows are within ± 7 days of the scheduled visit date for Weeks 3 through 48; however, visits should be at least 10 days apart, to ensure intervals of at least 10 days between study drug infusions. The visit window of ± 7 days also applies to assessments that cannot be performed on the same day; these assessments are considered part of that specific visit, and are to be labelled as such.

Subjects who complete the Week 48 visit may be eligible to participate in an optional OLE period where all subjects are offered continuing access to pamrevlumab treatment. The details of procedures and assessments, including visit window for OLE are described in Appendix 6.

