APPENDIX 2. PHARMACOKINETIC, BIOMARKER, IMMUNOGENICITY AND GENOMICS SAMPLING

Timepoint ^a	PK ^g (Plasma)	Biomarkers ^{b,f} (Serum and plasma)	CTGF ^b (Plasma)	HAHA/HAHA-NA ^e (Plasma)	Genomics ^{b,g} (Whole blood)	Tryptase (serum)
Day 1	X ^c	X	X	X ^b	X	
Day 8	X ^d					
Day 15	X ^d					
Week 3	X ^c					
Week 12	X ^c					
Week 24	X ^c	X	X	X ^b		
Week 36	X ^c		X	X ^b		
Week 48 /Last dose/ET	X ^c	X	X ^e	X ^b		
28 days after Last dose	X ^d	X	X ^f	X ^b		
Suspected Hypersensitivity/ Anaphylactic Reaction	X ^h		X ^h	X ^h		X ^h

Abbreviations: PK = Pharmacokinetic; CTGF = connective tissue growth factor; HAHA = human anti-human antibody; HAHA-NA = human anti-human antibody neutralizing antibody; ET = Early Termination

a.) For all time points, the actual date and time of sample collection must be recorded, in addition to date and time of study treatment administration.

b.) Sample should be collected within 2 hours prior to dosing start.

c.) Both pre-dose and post-dose samples are required for PK. Pre-dose sample collection should be within 2 hours prior to dosing and post-dose should be between 1-4 hours after dosing end.

d.) Only one sample is required. A ± 2 day window may be applied to the Day 8 and 15 sample.

e.) Samples with positive HAHA results will be tested for neutralizing antibody (HAHA-NA).

f.) Biomarkers will be collected in countries where the Regulatory Agencies allow collection of these samples.

g.) PK and DNA samples will be collected for subjects who consent, except in countries where the Regulatory Agencies do not allow collection of these samples

h.) In the event of a suspected hypersensitivity/anaphylactic reaction, PK, HAHA, HAHA-NA, CTGF and tryptase samples should be collected. The Tryptase sample should be drawn within 1 to 6 hours of immunogenic reaction, and all other samples should be collected within 24 hours of the immunogenic reaction.

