6.10.3. Clinical Implication of ADA Immune Response

6.10.3.1. PK

• Effect of ADA response on drug exposure will be explored by examining the drug exposures using graphical plots or simple summary statistics of observed drug concentration levels by ADA status and sampling time. Corresponding numerical values of geometric mean, arithmetic mean, and standard deviation will be displayed under the figures.

Confidential Page 36 of 56

• A listing of drug concentrations will be provided. Time course of observed concentrations by study visit with identifiers for antibody response will be plotted for each subject separately.

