Week 36	253	212	295
Week 48	337	296	351 [\$] or *[@]
28 days after last dose [\$]	365	Date of Last dosing+15 [\$]	* [\$]

^{\$} For subjects who do not enroll OLE only.

Note: If raw data shows visit is "28 Days post last dose", then set analysis visit=visit

Note: all assessments beyond 60 days post last infusion will be excluded from summary tables for labs.

Confidential Page 42 of 56

^{*} End of the double-blind period.

[@] For subjects who enroll OLE.

Table 10: Analysis Visit Window for SGRQ, UCSD-SOBQ, LCQ, PE, and Weight

Analysis Visit	Target Day	Start Day	End Day	
Baseline	Last value before the first study	alue before the first study drug infusion (or randomization date if no infusion received)		
Week 12	85	2	127	
Week 24	169	128	211	
Week 36	253	212	295	
Week 48	337	296	End of DBP	

Note: all assessments beyond 60 days post last infusion will be excluded from summary tables for PE.

Table 11: Analysis Visit Window for ECG

Analysis Visit	Target Day	Start Day	End Day
Baseline	Last value before the first study drug infusion (or randomization date if no infusion received)		
Week 48	337	2	End of DBP

Note: all assessments beyond 60 days post last infusion will be excluded from summary tables for ECG.

Table 12: Analysis Visit Window for Biomarkers (Serum and Plasma)

Analysis Visit	Target Day	Start Day	End Day
Day 1	1	1	1
Week 24	169	2	253
Week 48	337	254	351 [\$] or *[@]
28 days Post last dose [\$]	365	Date of Last dosing+15 [\$]	* [\$]

^{\$} For subjects who do not enroll OLE only.

Note: If raw data shows visit is "28 Days post last dose", then set analysis visit=visit

Note: all assessments beyond 60 days post last infusion will be excluded from summary tables.

Confidential Page 43 of 56

^{*} End of the double-blind period.

[@] For subjects who enroll OLE.

Table 13: Analysis Visit Window for CTGF and ADA (Plasma)

Analysis Visit	Target Day	Start Day	End Day
Day 1	1	1	1
Week 24	169	2	211
Week 36	253	212	295
Week 48	337	296	351 [\$] or *[@]
28 days Post last dose [\$]	365	Date of Last dosing+15 [\$]	* [\$]

^{\$} For subjects who do not enroll OLE only.

Note: If raw data shows visit is "28 Days post last dose", then set analysis visit=visit

Note: all assessments beyond 60 days post last infusion will be included in summary tables.

Table 14: Analysis Visit Window for Pharmacokinetic Concentration (Plasma)

Analysis Visit	Target Day	Start Day	End Day
Day 1	1	1	1
Day 8	8	2	11
Day 15	15	12	18
Week 3	22	19	52
Week 12	85	53	127

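### The last-measurement rule in SAP 5.5 does not exempt PK or CTGF, so by-visit PK summaries, read literally, keep post-dose values over paired troughs and can file early Week 3 samples under Day 15

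*SAP*

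**What the plan says.** **Selection rule.** SAP (double-blind) 5.5 sets aside the nominal CRF visits. Analysis visits "derived from visit dates and visit time windows will be used in the by-visit analyses", and unscheduled visits go to the nearest scheduled one. Then: "For subjects who have more than one measurement at a certain analysis visit, the last measurement will be used, with the following exceptions". Four exceptions follow: liver tests, spirometry, vital signs, and finally "ADA assessment: select in the order of 1) last ADA+ assessment; 2) earlier ADA+ assessment; 3) last ADA- assessment". Neither PK nor CTGF is listed.

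**Windows.** SAP Appendix 2, Table 14 has one row per PK visit and no timepoint label. Day 15 covers Days 12 to 18, Week 3 covers Days 19 to 52, and Week 12 covers Days 53 to 127. Table 6, for vital signs, labels its rows from Week 3 on as covering both predose and postdose.

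**Sampling.** Protocol Appendix 2 states "Both pre-dose and post-dose samples are required for PK" for Day 1 and Weeks 3, 12, 24, 36 and 48. The first is due within 2 hours before dosing and the second 1 to 4 hours after it ends. Single samples are taken on Day 8 and Day 15 (each ±2 days) and 28 days after the last dose. After a suspected hypersensitivity or anaphylactic reaction, PK and CTGF are drawn within 24 hours. Protocol 6.1.2 allows visits within ±7 days "of the scheduled visit date for Weeks 3 through 48".

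**Use.** SAP 6.10.3.1 explores the effect of ADA on exposure with plots or "simple summary statistics of observed drug concentration levels by ADA status and sampling time".

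**The concern.** A pre-dose and a post-dose concentration are different quantities and should not compete for one slot in a visit. A rule that keeps the later record always prefers the post-dose value of a complete pair. The trough is the exposure measure behind the dose: Protocol 2.6.2 argues that the chosen regimen "reaches the mean pamrevlumab trough where efficacy begins to plateau", at about 150 µg/mL. It is also the sample that responds more to faster clearance, which is how ADA would be expected to lower exposure. A by-visit comparison by ADA status built on post-dose values would use the less sensitive measure.

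Two further faults come from the date windows. The protocol's Week 3 window overlaps the Day 15 row of Table 14, and reaction-triggered samples fall into the same windows as scheduled ones.

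**Working it through.** **1. Table 14 boundaries.** Midpoints between adjacent target days reproduce the table:

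| Targets | Midpoint | Table 14 boundary |
|---|---|---|
| 8 / 15 | 11.5 | 11 / 12 |
| 15 / 22 | 18.5 | 18 / 19 |
| 22 / 85 | 53.5 | 52 / 53 (one day early) |
| 85 / 169 | 127 | 127 / 128 |
| 169 / 253 | 211 | 211 / 212 |
| 253 / 337 | 295 | 295 / 296 |

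The one-day discrepancy does not matter here.

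**2. Paired samples under the literal rule.** Take a completer in the PK sub-study who does not enter the OLE, sampled on target days.
- Scheduled samples: 6 paired visits × 2 + 3 single (Day 8, Day 15, 28 days after last dose) = 15.
- Kept, one per Table 14 row: 6 + 3 = 9.
- Not kept: 15 − 9 = 6, all pre-dose. Five are troughs (Weeks 3, 12, 24, 36 and 48). The sixth is the Day 1 pre-treatment sample, which is not a trough and arguably has its own rule through the baseline definition in SAP 5.3.2.
- An OLE entrant has no double-blind 28-day sample: 14 scheduled, 8 kept.

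A trough with no post-dose partner survives, for example after a missed post-dose draw. Likewise, a lone sample at an early-termination visit, where no infusion is given, is kept. One visit mean can then mix troughs and post-dose values.

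**3. Week 3 and Day 15.** Week 3 is allowed on Day 22 ± 7, that is Days 15 to 29 (15 days). Days 15, 16, 17 and 18 fall in the Day 15 row: 4 of 15 permitted days. The 10-day minimum between infusions does not prevent this, since Day 15 is 14 days after Day 1. Day 15 samples may be taken on Days 13 to 17, giving 5 × 15 = 75 permitted day pairs, of which 5 × 4 = 20 put Week 3 in the Day 15 row:
- 14 pairs: Week 3 is later, and its last sample replaces the true Day 15 sample.
- 3 pairs: same day, so clock time decides.
- 3 pairs: the Day 15 sample is later and is kept.

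In all 20 the Week 3 row has no scheduled sample. For example, a Day 15 sample on Day 15 and a Week 3 visit on Day 17 leave 8 records, with the Week 3 post-dose value standing as Day 15. These are counts of permitted combinations, not probabilities.

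**4. Reaction-triggered samples.** A PK sample after a reaction at Week 15 (Day 106) lies in the Week 12 window, Days 53 to 127. It is later than Day 85, so it replaces the Week 12 value. For CTGF, Table 13 gives Week 24 as Days 2 to 211, so a reaction sample at Week 27 (Day 190) replaces the Day 169 value.

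**5. Why the choice of sample matters (illustration only).** The documents give no half-life. Assume one compartment, steady state, dosing every 21 days, constant volume, and ADA doubling clearance. Let x = exp(−21k), where k is the elimination rate before doubling. Post-dose is proportional to 1/(1−x) and trough to x/(1−x). Doubling k turns x into x², so the post-dose value is multiplied by 1/(1+x) and the trough by x/(1+x).

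| Assumed half-life | x | Fall in trough | Fall in post-dose |
|---|---|---|---|
| 7 days | 0.125 | 89% | 11% |
| 14 days | 0.354 | 74% | 26% |
| 21 days | 0.500 | 67% | 33% |

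Doubling is a single assumed value, but the direction does not depend on it. Trough equals post-dose times x, and any rise in clearance lowers x, so the trough always falls by the larger proportion.

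**The case against.** The best reply is that 5.5 is a general rule and 6.10.3.1 is the specific one. The protocol defines pre-dose and post-dose as separate required samples, so a summary by sampling time can naturally be read as keeping them apart. Table 6 also weakens any inference from single rows: it does not split its rows but labels one window per visit with both timepoints, so the SAP can hold two timepoints in one visit row. TLF specifications are in a separate document and may already resolve this.

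That reading is available, but it does not settle the matter. Sampling time is undefined, Table 14 lacks the label that Table 6 carries, and 5.5 states an explicit selection rule with a closed list of exceptions. Nor does it cure the Day 15/Week 3 overlap or the reaction samples, which come from the windows.

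A reader might infer that all troughs are lost and an ADA effect on exposure would be hidden. The documents do not support that. The rule governs by-visit analyses only. SAP 5.1 puts all collected data in listings, and 6.10.3.1 adds a concentration listing and a time-course plot for each subject marked for antibody response. Population PK and exposure-response have their own plan (SAP section 1). Unpaired troughs are kept, and in the illustration the post-dose value still falls by 11% to 33%. The Day 15 replacement is also conditional: Week 3 must fall on Days 15 to 18 and after the Day 15 sample.

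**Conclusion.** The concern holds for by-visit PK and CTGF summaries. Applied literally, 5.5 and Table 14 drop the five paired on-treatment troughs, can mix troughs and post-dose values in one mean, can file a compliant Week 3 visit under Day 15 and leave Week 3 empty, and let reaction samples displace scheduled ones. At best, 5.5 and 6.10.3.1 leave the pre-dose/post-dose question to the programmer.

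The impact is limited. Scheduled PK is an optional sub-study in a subset of subjects at select sites, and the ADA-versus-exposure comparison is exploratory. Primary and secondary efficacy conclusions are unaffected. The sample counts rest only on the protocol schedule and the literal rule. The percentage falls rest on the assumed PK model, half-lives and doubled clearance, and serve only to show which sample is more sensitive.

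**What to change.** - In SAP 5.5, add PK concentrations and CTGF to the exceptions.
- Summarise PK by nominal visit and pre-dose/post-dose timepoint. This also removes the Day 15/Week 3 overlap.
- In Table 14, label the infusion visits with both timepoints, as Table 6 does for vital signs.
- In 6.10.3.1, define sampling time as nominal visit plus pre-dose/post-dose timepoint.
- List reaction-triggered PK and CTGF samples separately and leave them out of by-visit summaries.

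For the completer in the working, all 15 scheduled samples are then kept: 6 pre-dose, 6 post-dose and 3 single. The cost is a few lines of SAP text and table programming. Protocol Appendix 2, footnote a, already requires actual dates and times for sampling and dosing, so no new data are needed.

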6. STATISTICAL ANALYSIS

6.1. Subject Enrollment and Disposition

6.1.1. Eligibility Criteria

Eligibility criteria will be summarized for all screened subjects. The data will be summarized with respect to:

- number of subjects screened
- number (%) of subjects screen-failed
- number (%) of subjects for each failed inclusion/exclusion criterion

6.1.2. Subject Accountability and Disposition

Subject level inclusion criteria not met/exclusion criteria met listings will be provided.

The number (%) of subjects randomized (ITT), dosed (SAF), per-protocol set (PPS), Immunogenicity Analysis Set (IGS), completed the main study, entered the OLE period, and discontinued prematurely from treatment and study will be presented for each treatment group and all subjects pooled.

Reasons for premature discontinuation will be summarized by treatment group for the ITT population.

In addition, discrepancies between the randomization stratification factor derived from data in the Electronic Data Capture System (EDC) vs. data from the Interactive Response System (IRT) randomization system will be summarized. A listing will show any discrepancies between the two systems. If more than 5% discrepancies were identified, EDC randomization stratification factor will be used as fixed effects in the statistical analysis if applicable; otherwise, IRT randomization stratification factor will be used, unless otherwise specified.

